### 6.2 REPLACEMENT OF PARTICIPANTS

Subjects who withdraw or are lost to follow-up before completion of the first study intervention (first exercise prescription) will be replaced. Subjects who withdraw after the first study intervention do not need to be replaced. For patients lost to follow-up we will censor data collection at the last known date of contact.

### 6.3 LOST TO FOLLOW-UP

If the subject missed two consecutive scheduled follow-up time points and the attempts at contacting the subject detailed below are unsuccessful, then the subject is considered lost to follow-up. Site personnel shall make all reasonable efforts to locate and communicate with the subject (and document these efforts), including the following, at each contact point:

- A minimum of two reminder messages through the Pattern Health App.
- A minimum of two text messages to the patient's smart phone.
- A minimum of two telephone calls on different days over the specified follow-up windows to contact the subject should be recorded in the source documentation, including date, time, and initials of site personnel trying to make contact.
- If these attempts are unsuccessful, a letter (certified) should be sent to the subject.
- If a subject misses one or more non-consecutive follow-up contact time points, it will be considered a missed visit. The subject then may participate in subsequent visits. If the subject missed two consecutive time points and the above mentioned methods of communicating with the subject are unsuccessful, the subject will be considered lost to follow-up.

## 6.4 CRITERIA FOR DISCONTINUATION OF STUDY INTERVENTION

The study intervention will be discontinued if the occurrence of AEs exceeds the estimate used to calculate the risk benefit of study participation. The risks of participation are similar to those taken during exercise training occurring remotely currently at Duke University Health System.

## 6.5 CRITERIA FOR DISCONTINUATION OF AN INVESTIGATIONAL SITE

N/A

## 7 PARTICIPANT (STUDY) VISITS

### 7.1 PARTICIPANT SCREENING

Subject screening will begin after IRB approval, likely in December 2020.

Adult patients who are active in the Duke University Health System and with an Abbott Medical ICD or CRT-D device implanted between 01/01/2010 and 12/31/2020 will be screened by the study team for physical activity measures within the target range. In addition, the Duke EMR will be used to screen for EF measurement, medication use, and prior participation in CR. HF severity (NYHA class) and willingness to use a smartphone for study participation will be assessed using a survey or phone call to potentially eligible subjects.

### 7.2 CONSENT AND HIPAA AUTHORIZATION REQUIREMENTS

The nature of the study and its risks and benefits will be explained to the patient by the investigator or designated study personnel. The patient must voluntarily provide electronic informed consent on an ethics-approved informed consent form (ICF), prior to performing any study-related procedures.

Informed consent will be administered electronically through REDCap. The patient's electronically signed ICF will be stored in the study database.

### 7.3 INFORMED CONSENT FORM

See appendix 18.3.1

### 7.4 PARTICIPANT STUDY PERIODS

A patient will spend a total of 13 weeks in the study protocol: 1 week of baseline PA measurement prior to randomization and 12 weeks of intervention or control care. The study visit table is below in section 8.3

### 7.5 DISCHARGE OF PARTICIPANT

Prior to discharge from the protocol participants will complete the NYHA assessment and KCCQ QOL assessment, an assessment of AEs, a remote monitoring transmission, and a review of medications.

The subject will be encouraged to use the Garmin device to continue to achieve similar PA thresholds to what were accomplished in the last follow up period.

### 7.6 FOLLOW-UP VISITS

All follow-up visits will occur through the Pattern Health App. Any AEs will be self reported and further details will be acquired by telephone call as needed.

## 8 STUDY PROCEDURES

### 8.1 STUDY DURATION AND TIMELINE

Table 2: *Study Duration*

	Deliverable	Proposed Submission Date
1	Planning/IRB Approval	11/30/20
2	Last Patient Enrolled	12/30/20
3	Last Patient Last Visit	5/31/21
4	Database Lock	6/30/21
5	Final Analysis Complete	7/30/21
6	Manuscript Submission	8/31/21

### 8.2 PARTICIPANT MEDICAL HISTORY

Targeted Medical History will be collected at baseline.

The following elements of past medical history will be collected to describe the patients and ensure randomization was effective at balancing covariates of interest:

- Etiology of HF (ischemic versus non-ischemic)
- LVEF
- Baseline NYHA Class
- Previous Revascularization
- History of MI
- Moderate or Severe Valvular Disease (Aortic or Mitral)
- Baseline Medications (ACE Inhibitor, Beta blocker, ARNI, digoxin, loop diuretic, statins)
- Diabetes
- Hypertension
- BMI
- A fib or A flutter
- PHQ-9 Depression Screen
- Baseline Systolic and Diastolic BP (measured by cuff at home)
- Device type (ICD versus CRT-D)
- Baseline daily PA duration (minutes)
- Baseline day and night heart rate

### 8.3 PARTICIPANT SCHEDULE OF EVENTS

See appendix 18.1

## 8.4 STUDY INTERVENTIONS

### 8.4.1 BASELINE

After confirmation of eligibility and Informed Consent, the participant will receive a Garmin wearable device and download the CR app (Pattern Health). The Garmin device will be linked to the CR App, and patients 1 month prior to randomization will be used to collect a baseline physical activity level.

Following the baseline month, patients will be randomized 1:1 to either remote CR or usual care through the CR app.

### 8.4.2 TREATMENT

Remote CR: Patients randomized to remote CR with usual care will receive the complete suite of Duke Health remote CR features. They will be asked to use the app a minimum of 3 times a week but can use it more often if they prefer. A typical CR session will involve a series of questions screening for symptoms including chest pain or shortness of breath at rest. Patients will be asked to input their morning weight, resting blood pressure (from a home cuff, ) and their morning blood glucose level (if diabetic). After this data is provided, patients will be given an exercise prescription provided by a certified exercise physiologist based on the patient inputs, resting heart rate, prior prescriptions, and mean physical activity measured by the ICD or CRT device over the past 1 week.

The exercise prescription will change each week based on refreshed data from the prior week. Abbott devices are capable of measuring not only the total daily exercise time but also the intensity of the exercise performed (categorized as none, light, moderate, and vigorous). Total time in each intensity bin is logged in the device and transmitted to Merlin. The exercise physiologist will create the prescription to increase not only the total amount of exercise time but also the intensity of exercise, such that patients gradually increase the amount of time spent in each exercise intensity bin.

Instructional videos for each exercise are provided in the app. Patients will not be told to perform the exercise at a particular time. Instead they will be asked to complete a certain amount of exercise per week at whatever time is convenient for them. Exercises will be prescribed to accommodate certain disabilities. Examples include walking for a patient with normal ambulation, resistive arm exercises for patients who require the use of a cane or walker for ambulation, etc. Patients will be asked to wear the Garmin throughout the day and are free to track their own heart rate and step count, but no step count goal will be provided. The Garmin account will initially be set up by the study team and Garmin data will be cataloged and used for study endpoints. At the conclusion of the study the Garmin account will be turned over to the patient and they will be given the Garmin as a gift for participation in the study. Patients randomized to remote CR will also receive App based reminders to take their medications, resources to guide healthy eating habits, and other behavioral health advice as is done as standard of care in both remote based and clinic based CR. Each week they will receive visual feedback on the smartphone app summarizing their progress in CR. Presented data will include their change in physical activity compared to the prior weeks and change in weight from prior weeks. At the beginning of week 1 and the end of week 12 the smartphone app will also perform the KCCQ quality of life questionnaire.

Patients randomized to remote CR will complete a self-administered satisfaction survey through the app at the end of week 12. Results of the survey will be used for program improvement and feasibility.

Usual Care: Patients randomized to usual care will receive the App and Garmin device but will not be provided with the full suite of features. They will be asked to log into the app at least 3 times a week. They will be given the same series of questions as patients randomized to remote CR screening for symptoms including chest pain or shortness of breath at rest. Patients will then be asked to input their morning weight, resting blood pressure (from a home cuff, if they own one) and their morning blood glucose level (if diabetic). No further information will be presented to the patient but they will be encouraged to continue to pursue a healthy lifestyle and to contact their physician if they are experiencing worsening symptoms of heart failure. At the beginning of week 1 and the end of week 12 the App will also perform the KCCQ quality of life questionnaire.

## 9 STUDY OUTCOMES

### 9.1 AIMS

**Aim 1:** Compare the mean Abbott ICD and CRT-D device measured daily PA obtained over the 1 week before randomization (baseline) and 12 weeks after randomization among patients randomized to remote CR versus usual management. This objective was chosen to determine if it is possible to objectively measure a clinically meaningful change in PA using an ICD or CRT-D device. Further, the primary objective assesses whether a remotely administered exercise training program can increase the observed PA over a relatively short time interval.

**Aim 2:** Compare baseline and 12 week Kansas City Cardiomyopathy Questionnaire (KCCQ) HF symptom severity scores among patients randomized to remote CR versus usual management. This objective was chosen to determine if the remotely administered exercise training is associated with subjective improvement in HF symptoms. This endpoint has been used previously in studies of exercise training in patients with HF, so we should be able to compare the direction and magnitude in change in our study to results obtained in prior studies.

**Aim 3:** (Safety) Report Adverse Events of heart failure hospitalization, fracture, myocardial infarction, serious adverse arrhythmia, and ICD therapy among patients randomized to remote CR versus usual management. This objective is important since little data are available regarding the safety of starting an exercise training program without a prior CPET study. We will determine if patients randomized to exercise training experience excess risk.

**Aim 4:** Measure the correlation between change in daily PA measured by the Abbott ICD or CRT-D device between baseline and end of follow up and change in KCCQ HF symptoms severity score measured between baseline and end of follow up. This objective will allow us to determine what change in device measured PA is associated with an improvement in QOL.

The results of this study (Aims 1-4) will be used to design a larger pivotal randomized controlled study evaluating whether remotely administered CR reduces the combined clinical endpoint of HF related hospitalization or death. Providing CR using a smartphone app coupled to an existing implantable device may result in significant cost savings and improved availability, particularly to vulnerable populations. This study would support label expansion for ICD and CRT-D devices to include provision of remotely administered CR and would be used in support of a new coverage for implantable device guided remotely administered CR.

### 9.2 DEFINITIONS

#### 9.2.1 ABBOTT ICD AND CRT-D DEVICE MEASURED PA

Physical activity is defined as a force measurement of 25 mg as measured by the Abbott Medical ICD or CRT-D implantable device. The accelerometer within the Abbott medical cardiac electronic implantable device detects both the frequency and amplitude of patient motion to calculate a force measurement. A force measurement of 25 mg is equivalent to walking 2 miles per hour.

#### 9.2.2 KCCQ AND NYHA SCORES

The Kansas City Cardiomyopathy Questionnaire (KCCQ) will be completed by the participant via the Pattern Health CR App prior to starting intervention and after 12 weeks of intervention.

The KCCQ is a 23-item, self-administered, validated and reliable questionnaire, measuring the patient's perception of their HF symptoms and how their HF affects their quality of life. KCCQ scores range between 0 and 100, with 100 representing the least burden of symptoms. The NYHA scale is well validated and reproducible. We will use a previously validated version in the study.

### 9.2.3 ADVERSE EVENTS OF SPECIAL INTEREST

AEs of special interest (AESIs) defined for this trial include: heart failure hospitalization, fracture, myocardial infarction, serious adverse arrhythmia, and ICD therapy. Certain disease-related events (DREs) that are common within the study population will not be reported. This includes chest pain, hyper or hypotension, hyper or hypoglycemia, muscle or joint pain, shortness of breath or breathlessness, fatigue, diaphoresis, or depression.

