#### 14.2.2 DEFINITION OF A SERIOUS ADVERSE EVENT

An adverse event (or a suspected adverse reaction) is considered "serious" if it has been determined by either the investigator or sponsor that a particular event results in the following outcomes: a life-threatening adverse event, significant or persistent state of incapacitation (or severe disruption of normal daily functions), a congenital anomaly/birth defect, inpatient hospitalization (or lengthened hospitalization) or death. In the event important medical events that do not result in death (but require hospitalization or is life threatening) can be classified as a serious adverse event with appropriate medical judgement when interventions related to the study jeopardize the study participant (and

require medical or surgical intervention to prevent any of the outcomes listed in the definition of a serious adverse event).

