#### 14.2.3 CLASSIFICATION OF AN ADVERSE EVENT

The following categories will be used to classify AE in the protocol.

- **Mild** – Events that will require minimal or no treatment intervention and does not interfere with the participant's daily activities.
- **Moderate** – Events that could result in a low-level inconvenience or concern with the prescribed therapeutic measures. A moderate event may cause interference with normal functioning.
- **Severe** – Events that can interrupt a study participant's typical daily activity and would require systemic drug therapy or another intervention/treatment. Severe events can pose as potentially life-threatening or incapacitating. Note, the terms severe and serious are not necessarily equal.

Relatedness: AEs that result from the presence, application, or performance of the remotely administered exercise regimen will be considered system related. AEs that are not temporally related, that affect organ systems or body-sites that are not affected by the exercise regimen, or that can be attributed to another cause will be considered unrelated.

Adverse Event relationships to the study intervention will be classified as either related to study participation or not related to study participation. Expected and unexpected AEs will be clearly delineated from one another. Expected AEs include worsening HF symptoms, orthopedic injury (including fracture, sprain, or tear of bone or soft tissue), myocardial infarction, serious arrhythmia, and ICD therapy. All other AEs will be considered unexpected.

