#### 14.2.4 ADVERSE EVENT REPORTING

Timely, accurate, and complete reporting and analysis of safety information for clinical studies are crucial for the protection of subjects. Reporting and analysis of safety data are mandated by regulatory authorities worldwide. AE CRF's will be collected for all AEs that are potentially study-related and all serious AEs regardless of their relationship to the study. For AEs that require immediate reporting, initial reporting may be done by phone, fax, email or on the CRF completing as much information as possible. The AE CRF must be completed as soon as possible. For any changes in status of a previously reported adverse event (i.e. change in actions taken, change in outcome, change in relatedness), an update to the original AE must be completed. All reported AEs must be followed until the AE has been resolved, is unresolved with no further actions planned, the subject dies or exits the study, or until study closure, whichever occurs first. In the event that a subject is exited from the study prior to study closure, all efforts should be made to continue following the subject until all unresolved system related AEs, as classified by the investigator, are resolved or they are unresolved with no further actions planned. At the time of study exit, all collected AEs with an outcome of "Unresolved, further actions or treatment planned" must be reviewed and an update to the original AE must be reported. At a minimum, if there are no changes to the description, relatedness, test and procedures or actions taken, the outcome must be updated to reflect "Unresolved at time of study closure."

All AEs will be reported to the sponsor and the IRB within 10 working days of the event.

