#### 14.2.5 SERIOUS ADVERSE EVENT REPORTING

Regulatory reporting of AEs/device deficiencies will be completed according to local regulatory requirements. Refer to Table 4: SAE reporting timeframes for a list of required investigator reporting requirements and timeframes. The investigator is required to report all SAE's to the Sponsor immediately, and to the IRB per local requirements. The sponsor is also required to report these events to the local regulatory authority based on their requirements. It is the responsibility of the investigator to abide by any additional AE/device deficiency reporting requirements stipulated by the IRB responsible for oversight of the study. For AEs/device deficiencies that require immediate reporting, initial reporting may be done by contacting the study sponsor per the sponsor contact information provided in this document.

*Table 4: SAE reporting timeframes*

Serious Adverse Events	
Investigator submit to:	
Sponsor	Immediately
IRB	Per local IRB requirement
NESTcc	Immediately
Sponsor submit to:	
Regulatory authorities	Per local requirement
IRB	Per local IRB requirement

All SAEs will be followed and tracked until there is a satisfactory resolution or the site investigator uses their medical judgement to classify the participant as stable or suffering from a chronic illness.

According to 21 CFR 312.32(c)(2), “the FDA must be notified of any unexpected fatal or life-threatening suspected adverse reaction as soon as possible but in no case later than 7 calendar days after the sponsor's initial receipt of the information.”

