## 15 RISK BENEFIT AND CONFIDENTIALITY

## 15.1 RISK/BENEFIT ASSESSMENT

Study subjects randomized to the intervention study arm will perform more PA than normal for the 12 weeks of study participation. During this time, they may be subject to increased risks of muscle or joint strain, fracture, fall, or soft tissue swelling or pain. Additionally, study subjects may have a higher risk of heart failure hospitalization, myocardial infarction, serious adverse arrhythmia, and ICD therapy. There are no expected long-term risks. Risks will be minimized by designing an exercise regimen that provides small incremental increases in physical activity and further increases will be guided by feedback provided by subjects through the Pattern Health application.

Participation in the research study may have potential benefit. Prior retrospective studies suggest that increased PA is associated with improved 1-5 year survival and reduced risk of hospitalization in patients who meet study inclusion criteria. Further work suggests that increased PA is also associated with reduced frequency and severity of depressive symptoms.

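### Protocol 9.2.3 exempts eight symptom groups from reporting without limiting this to non-serious, unrelated events; this is at odds with 10.1.1, 14.2.4 and 14.2.5, and no text says which rule prevails

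*Protocol*

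**What the plan says.** Protocol 9.2.3 names five AEs of special interest: HF hospitalization, fracture, MI, serious arrhythmia and ICD therapy. It then adds: "Certain disease-related events (DREs) that are common within the study population will not be reported". The list that follows covers chest pain, high or low blood pressure, high or low blood sugar, muscle or joint pain, breathlessness, fatigue, sweating and depression. The section says nothing about seriousness or relatedness and does not refer to Section 14.

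Elsewhere the protocol sets these duties, none of which mentions an exemption:

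- 10.1.1: every AE is entered in the eCRF.
- 14.2.4, on CRFs: "AE CRF's will be collected for all AEs that are potentially study-related and all serious AEs regardless of their relationship to the study".
- 14.2.4, on onward reporting: "All AEs will be reported to the sponsor and the IRB within 10 working days of the event".
- 14.2.5: "The investigator is required to report all SAE's to the Sponsor immediately, and to the IRB per local requirements".

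Three further sections bear on how these rules meet. Section 14.2.2 defines seriousness by outcome, and the outcomes include "inpatient hospitalization (or lengthened hospitalization) or death". Section 14.2.3 gives a relatedness test: "AEs that result from the presence, application, or performance of the remotely administered exercise regimen will be considered system related", while events with no temporal link, at body sites the regimen does not affect, or explained by another cause are unrelated. Section 15.1 says of patients in the exercise arm that "they may be subject to increased risks of muscle or joint strain, fracture, fall, or soft tissue swelling or pain".

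The SAP (6.4, S2) plans a listing of the five special-interest events and does not mention the exemption.

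**The concern.** Two coordinators could each follow the protocol and handle the same event in opposite ways. One reads 9.2.3 and does not report it; the other reads 14.2.4 and sends it to the sponsor and IRB. The protocol does not say who is right.

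This matters because several of the exempt symptoms are ones that exercise might provoke, and Aim 3 (9.1) notes how little is known about the safety of starting exercise training without a prior CPET. Sections 10.3 and 12.5 state that there is no DSMB, so reports to the sponsor and IRB carry more of the ongoing oversight.

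**Working it through.** No figure in the plan is in question. The check consists of counts from the text and a comparison of the rules case by case.

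**Counts.**
- Symptom groups exempt under 9.2.3: 8.
- Special-interest events: 5. Number of these on the exempt list: 0.
- Duties stated elsewhere with no matching exception: 1 (10.1.1) + 2 (14.2.4) + 1 (14.2.5) = 4.
- Limits on seriousness or relatedness in 9.2.3: 0.
- Statements of precedence in the protocol or SAP: 0.

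**The listed symptoms are AEs.** Section 14.2.1 defines an AE as any untoward medical occurrence, whether or not the intervention caused it. A rule that covers all AEs therefore covers these symptoms unless an exception is written.

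**The rules side by side.** Each row is an event on the 9.2.3 list.

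| Event | 9.2.3 | 10.1.1 | 14.2.4, CRF | 14.2.4, 10 days | 14.2.5 |
|---|---|---|---|---|---|
| Non-serious, unrelated (fatigue from HF) | not reported | record | not required | report | does not apply |
| Non-serious, potentially exercise-related (joint pain after a session) | not reported, if applied by symptom name | record | required | report | does not apply |
| Serious, unrelated (admission for hypotension) | not reported, if applied without regard to seriousness | record | required | report | report at once |
| Serious, potentially exercise-related (admission for chest pain without MI) | as the two rows above | record | required | report | report at once |

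**Row 1** conflicts on the plain words. The CRF sentence in 14.2.4 does not reach such an event, but the 10-day sentence does, and 10.1.1 requires an eCRF entry.

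**Row 2** depends on what the label disease-related means. If it is a causal limit, joint pain from exercise falls outside the exemption. If staff go by the symptom name, it falls inside, although 15.1 names muscle or joint strain and soft tissue pain as risks of the exercise arm. Section 14.2.3 also classes neighbouring events as expected AEs: "Expected AEs include worsening HF symptoms, orthopedic injury (including fracture, sprain, or tear of bone or soft tissue"), among others. That overlap is only partial, since a sprain or tear is not the same as pain.

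**Rows 3 and 4** depend on whether staff read a list of symptoms as also covering admissions for those symptoms. An admission that qualifies as HF hospitalization or MI is still captured as a special-interest event. An admission for hypotension, low blood sugar or chest pain without MI is not on that list, so its reporting rests on Section 14 alone.

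**The case against.** The strongest reply is context. The sentence stands in a section of outcome definitions, under the special-interest heading and directly after the five events. It may mean only that these symptoms are not reported as part of that outcome, while Section 14 governs reporting. That may well be the intent, but the sentence does not say so. The five events are already listed, so on this reading it would add almost nothing.

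A reader might infer that the protocol instructs staff to withhold serious events. The documents do not support that. Section 9.2.3 never mentions serious events or admissions. Section 14.2.4 covers serious AEs whatever their relationship to the study, and 14.2.5 repeats the duty. For an SAE to be missed, staff would have to let a sentence in an outcome definition override those explicit instructions. This is possible, because a specific list is easily taken as an exception to a general rule, but it is not what the text plainly orders.

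A reader might also infer that staff have no means of separating disease from exercise as the cause. They do: 14.2.3 supplies a test. The gap is that 9.2.3 does not invoke it and exempts by symptom name.

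Finally, detection is not lost. Both arms answer the same app questions on chest pain and resting breathlessness (8.4.2), the app asks about recent hospitalization (10.1.1), and the EMR is screened at study conclusion for unreported AEs (10.1). This stands, but only in part. An answer to a screening question is not an AE report, and a search at study conclusion is too late for immediate SAE reporting. It can also be said that 10.1.1 concerns recording and 9.2.3 concerns reporting, so both could be met by recording without reporting. The 10-day sentence in 14.2.4 leaves no such way out.

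**Conclusion.** The concern holds as a contradiction between sections. For non-serious events on the list it is certain: 9.2.3 says they are not reported, and 14.2.4 says all AEs are. For serious admissions that are not HF hospitalization or MI, and for exercise-related muscle or joint pain, under-reporting is a possibility. It rests on the assumption that staff treat 9.2.3 as the specific exception.

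The extent is eight symptom groups against four duties. No number of lost reports can be given, because the documents state no event rates.

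A reader might infer that the comparison of safety between arms, or the discontinuation rule in 6.4, would be distorted. Neither can be shown. Section 3.2 speaks generally of reporting AEs between groups, but Aim 3 and S2 make this specific as the five special-interest events, none of which is exempt. Section 6.4 depends on the occurrence of AEs exceeding an estimate that it does not state, so no changed decision can be demonstrated. The primary endpoint is not touched.

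The correction is still worth making: the ambiguity concerns patient safety, there is no DSMB, and a wording change removes it.

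**What to change.** Reword 9.2.3 along these lines: *Events on this list that are non-serious and judged unrelated to the exercise regimen under Section 14.2.3 need not be recorded or reported as AEs. Any event on this list that is serious, or potentially related to the exercise regimen, is recorded and reported under Sections 14.2.4 and 14.2.5, in both arms.*

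In 14.2.4 and 10.1.1, name this exemption as the only exception to the sentences that cover all AEs. No new relatedness test is needed, and the SAP does not have to change.

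Exempting common, non-serious, unrelated symptoms is legitimate, and this wording keeps that. The cost is the rewording, two cross-references and a few more minor AE entries in a single-center study planned for 50 patients. No visit or analysis is added.
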